4.3 Safety outcomes: Adverse events of special interest (AESI)

Each of the AESI including AMI, PE, DIC, ITP will be assessed separately in the analysis by vaccine brand. The diagnosis of AESI will be identified with International Classification of Diseases, Tenth Revision, Clinical Modification (ICD-10-CM) codes (Appendix Table 1). The settings in which each outcome will be evaluated, as well as the clean (washout) and risk windows for each AESI are described in Table 3. The first occurrence of the event is defined as an incident AESI only if no event was recorded during the preceding pre-defined interval or the clean window. The risk window is defined as an interval post-vaccination during which occurrence of the AESI may be associated with the vaccine exposure. Both clean and risk windows are selected based on the literature and consultation with subject matter experts.

Table 3. AESI, settings, clean windows, and risk windows

AESI	Care Setting	Clean Window	Risk Window
Acute Myocardial Infarction (AMI)	IP	365 days*	1-28 days ^{4,5}
Pulmonary Embolism [#] (PE)	IP, OP/PB	365 days*	1-28 days ⁶⁻⁸
Disseminated Intravascular Coagulation (DIC)	IP, OP-ED	365 days*	1-28 days ⁹
Immune Thrombocytopenia (ITP)	IP, OP/PB	365 days*	1-42 days ^{10,11}

* Selection of clean window duration is based on clinician input.

[#] The PE onset date is determined by the date the PE code is reported in the database.

5 Study Design

5.1 Self-Controlled Methods

The SCCS design^{12,13} compares the incidence of adverse events within periods of hypothesized excess risk due to exposure (risk interval) with incidence during all other times (control interval). In SCCS, only cases

(i.e., individuals with an incident AESI) occurring during the study observation period are sampled, with estimation of risk occurring within individuals rather than between individuals. Created to assess the risk of acute events in clearly defined risk intervals, this design implicitly controls for measured and unmeasured time-invariant confounding as each case serves as his/her own control. To address the concern that the occurrence of the AESI may possibly affect the likelihood of subsequent vaccination, we will limit the control intervals for the primary analysis to post-vaccination only. To minimize exposure misclassification, we will restrict the study population to cases receiving COVID-19 vaccines.

The SCRI design is a special case of SCCS. In SCRI, a person's risk of experiencing the outcome immediately after exposure (risk interval) is compared to the same person's risk of experiencing the outcome in a discretely defined period (control interval), during which the occurrence of AESI is deemed to be unrelated to the exposure. Unlike the standard SCCS design, the SCRI method requires defining a specific time interval within the observation period as the control interval. Compared to SCCS, SCRI may be less affected by time-varying confounding due to the shorter control interval, while the shorter control interval may reduce statistical power.

The control intervals in both designs can be defined as pre- and post-vaccination, and both have strengths and limitations. A pre-vaccination control interval can facilitate timely analyses. However, the pre-vaccination control interval is subject to bias if the occurrence of the AESI affects the probability of subsequent vaccination, biasing the relative incidence in either direction. If the event only temporarily delays vaccination or increases the probability of vaccination, a pre-exposure period can be excluded to reduce the healthy vaccinee effect. Post-vaccination control intervals will avoid such a bias of reverse causation but require additional data accrual after the post-vaccination risk window, resulting in an analysis delay; the delay of the analysis is greater for AESI with longer risk intervals.

5.2 Overview of Study Design

This protocol will use the SCCS design with post-vaccination control intervals as the primary analysis. This design is not subject to the bias from depletion or enrichment of AESI cases in the pre-vaccination control interval. However, it relies on an accurate definition of the risk window, which remains unknown following COVID-19 vaccination for each AESI. Inaccurate attribution of cases to the risk or control intervals may bias the risk estimate in either direction based on the shape of the underlying risk function of the AESI following vaccination. For example, for events with a late onset, attributing cases to the control intervals that should have been attributed to the risk interval may underestimate the relative risk. Sensitivity analyses, such as temporal scan, are proposed in Sections 5.7.2.1 and 5.7.3.1 to assess the robustness of risk intervals. Also, using post-vaccination control intervals will require additional data accrual following the post-vaccination risk interval, and this will delay the analysis.

The secondary analysis will use the SCCS design with control intervals around vaccination, including pre- and post-vaccination time other than the pre-specified risk interval (Table 3), during the observation period. This design has greater statistical power, compared with the primary analysis, by including more AESI cases. However, it is subject to the reverse causation bias from depletion or enrichment of AESI cases in the pre-vaccination control interval because the occurrence of an AESI during the observation period may affect the likelihood of subsequent vaccination. For example, if an AESI reduces the probability of subsequent vaccination, the relative incidence associated with vaccination will be biased upwards. It is

also subject to the same bias as the primary analysis from inaccurate definition of the risk window in the post-vaccination period.

The exploratory analysis will use the SCRI design with only a pre-vaccination control interval. This design can provide more timely results, compared with the primary analysis. However, it is subject to the same reverse causation bias described above from depletion or enrichment of AESI cases in the pre-vaccination control interval. This analysis is performed for comparison purposes to understand the magnitude and direction of the potential bias this study design may create in the measure of association.

This study will be implemented for each pre-defined AESI by vaccine brand (i.e., Pfizer-BioNTech, Moderna, and Janssen). A sample of medical charts for each AESI will be obtained and adjudicated to confirm the diagnosis of the outcome of interest.

5.3 Study Period

The study period will start on the date of the emergency use authorization for the first COVID-19 vaccine in the U.S. (December 11, 2020 for Pfizer-BioNTech vaccine) and will end on the date through which complete claims data (defined as at least 90% complete) are available for the data source at the time of study initiation.

The completeness threshold was selected to balance the potential bias due to partially accrued observation of post-vaccination control intervals versus risk intervals, and a reasonable delay of the analysis. The 90% completeness is likely to overestimate relative risk by 10% or less. Assuming that event observation delays are accurately estimated from historical data, a 90% completeness threshold limits the difference in observation of events in risk intervals (at most 100% complete) versus control intervals (at minimum 90% complete). If the true RR is 1, the bias due to observation delay is $(100\%/90\%) - 1 = 11\%$. However, in practice risk and control interval completeness will fall between 100% and 90% and we expect the potential bias due to claims delay to be smaller.

[figure not shown]
5.4 Definition of Risk and Control Intervals

The risk interval is defined as the time during which excess risk is hypothesized following each COVID-19 vaccine dose for the AESI based on biological plausibility and clinical input (Table 3). The selected risk intervals are AESI-specific and are determined based on review of literature and consultation with subject matter experts. Post-first dose risk intervals will run until the end of the interval, or until the person receives his/her second dose (if within the risk interval). Post-second dose risk intervals will run until the end of the risk interval.

5.4.1 Primary Analysis: SCCS with Post-vaccination Control Intervals

The observation period will start from the vaccination date (day 0) of the first dose, if there are two doses, and extend to day 90. The post-vaccination control interval is defined as all follow-up time during the observation period following either the first or second COVID-19 vaccine dose (for two-dose COVID-19 vaccines) that is outside of the risk interval(s) until day 90 post-vaccination, end of study period, disenrollment, or death, whichever occurs first; while likely uncommon, this includes any time between the end of the first dose risk window and the receipt of a second dose. Figure 1 presents some hypothetical examples in design. Individuals who only accrued data during the risk intervals will be ineligible to be included in the analysis (Section 5.5.1).

Figure 1. Hypothetical examples of SCCS design with post-vaccination control intervals for one-dose and two-dose vaccines

[figure not shown]

Note: The hypothetical risk interval following one dose is up to 28 days. However, the length of the risk and control intervals will vary for each AESI.

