2.1 Primary Analysis

Evaluate the risk of AMI, PE, DIC, and ITP after exposure to each COVID-19 vaccine using the self-controlled case series (SCCS) design. The primary analysis compares the risk of each event in a time

interval after vaccination (risk window) to that in time intervals post-vaccination after completion of the risk window (control window) within the study period.

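### Read literally, the primary analysis counts the day of the first dose as control time, against section 2.1, and leaves the day of the second dose unassigned

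*Protocol*

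**What the plan says.** Section 5.4.1 states: "The observation period will start from the vaccination date (day 0) of the first dose"; the period runs to day 90. Control time is "all follow-up time during the observation period following either the first or second COVID-19 vaccine dose" "that is outside of the risk interval(s) until day 90 post-vaccination, end of study period, disenrollment, or death, whichever occurs first". Table 3 gives risk windows of days 1-28 (AMI, PE, DIC) and days 1-42 (ITP), so day 0 is in no risk window. Section 5.4.2 takes over the same post-vaccination control intervals for the secondary analysis. Its 14-day pre-exposure exclusion covers the days before vaccination, not day 0.

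Two other places point elsewhere. Section 2.1 describes the primary comparator as "time intervals post-vaccination after completion of the risk window (control window"), which would leave out day 0 of dose 1. Exclusion (ii) in section 5.5.1 removes people who are censored in the risk window before they have any post-vaccination control time.

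For the second dose, section 5.4 says "Post-first dose risk intervals will run until the end of the interval, or until the person receives his/her second dose", when that dose falls inside the interval. It does not assign the dose-2 day itself. The dose-stratified sensitivity analysis in section 5.7.2.1 has a category in which the two risk intervals overlap.

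**The concern.** Control time should represent the rate that cases would have had without vaccination. Day 0 does not, for two reasons that act in opposite directions. Someone admitted with an AMI or PE that morning is unlikely to be vaccinated later that day, so events may be depleted, the control rate too low and the RR too high. This is the same selection for which section 5.4.2 drops the 14 days before vaccination. On the other side, vaccination during a care encounter, or a reaction on the same day, puts events on day 0, so the control rate is too high and the RR too low. Where claims give only a date, they cannot order a same-day event and dose; the Table 3 footnote dates PE by the day its code is reported.

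The literal rule also undoes the plan's own eligibility rule. If day 0 is control time, everyone followed beyond day 0 has control time before the risk window opens, and the censoring part of exclusion (ii) would remove none of them. That suggests the authors did not intend it, but the text from which the analysis will be programmed says it.

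The planned sensitivity analyses do not repair this. The carry-over exclusions in sections 5.7.2.1 and 5.7.3.1 remove only days after the risk interval. The day-by-day plot in section 5.7.1 might show a dip or spike on day 0 but changes no estimate.

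**Working it through.** **1. The plan's own figure: Table 6.** Inputs from section 5.8: two-sided alpha 0.05, power 80%, 28 or 56 risk days, RRs of 1.42, 1.54, 1.91 and 1.44, and a stated observation period of 90 days. The formula is the SCCS signed-root likelihood-ratio sample size. With r = risk days / observation days and p = r·RR/(r·RR + 1 − r):

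- A = 2[p·ln RR − ln(r·RR + 1 − r)]
- B = (ln RR)²/A × r·RR(1 − r)/(r·RR + 1 − r)²
- n = (1.960 + 0.842·√B)²/A, rounded up

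Example, AMI with r = 28/91: p = 0.387, A = 0.0283, B = 1.031, n = 280.1, so 281.

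| | AMI | PE | DIC | ITP |
|---|---|---|---|---|
| Table 6 (28 / 56 days) | 281 / 286 | 183 / 191 | 79 / 89 | 259 / 265 |
| 91 observation days | 281 / 286 | 183 / 191 | 79 / 89 | 259 / 265 |
| 90 observation days | 279 / 288 | 182 / 193 | 79 / 90 | 258 / 267 |

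All eight figures match with 91 days (days 0 to 90). With the stated 90 days one of eight matches, and the rest are within 2 cases. This is consistent with one extra non-risk day. It is not proof.

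**2. Control days.** Count days 0-90 from dose 1, with dose 2 at the Table 2 intervals (day 21 for Pfizer-BioNTech, day 28 for Moderna). C is the number of control days with every day 0 left out:

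- Pfizer-BioNTech: days 50-90, C = 41 (28-day window); days 64-90, C = 27 (42-day window)
- Moderna: days 57-90, C = 34; days 71-90, C = 20
- Janssen: days 29-90, C = 62; days 43-90, C = 48

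**3. Shift in the RR.** Let k be the number of day 0s counted as control and f the day-0 event rate relative to baseline. The control rate is multiplied by (C + k·f)/(C + k), so the RR is multiplied by (C + k)/(C + k·f). The protocol gives no f; the values below are assumptions.

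| | k=1, f=0 | k=1, f=3 | k=2, f=0 |
|---|---|---|---|
| Pfizer-BioNTech, 28 d | 42/41 = 1.024 | 42/44 = 0.955 | 43/41 = 1.049 |
| Pfizer-BioNTech, 42 d | 28/27 = 1.037 | 28/30 = 0.933 | 29/27 = 1.074 |
| Moderna, 28 d | 35/34 = 1.029 | 35/37 = 0.946 | 36/34 = 1.059 |
| Moderna, 42 d | 21/20 = 1.050 | 21/23 = 0.913 | 22/20 = 1.100 |
| Janssen, 28 d | 63/62 = 1.016 | 63/65 = 0.969 | n/a |
| Janssen, 42 d | 49/48 = 1.021 | 49/51 = 0.961 | n/a |

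Half depletion (f = 0.5, k = 1) gives 0.8% to 2.4%.

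**4. Secondary analysis.** The pre-vaccination control interval adds 28 or 42 days to C, so with k = 1 and f = 0 the factor falls to 70/69 = 1.014 (Pfizer-BioNTech), 63/62 = 1.016 (Moderna) and 91/90 = 1.011 (Janssen), for either window.

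**The case against.** The strongest reply is that the protocol is inconsistent here rather than settled. Section 2.1 excludes day 0 of dose 1 from control, and section 5.4.1 speaks of follow-up after a dose, which can be read as starting the next day. Figure 1, which draws the intervals, is not available to decide it. That stands, and it is why the point is put as a conflict to resolve. It does not remove the problem, because the detailed definition in section 5.4.1, applied as written, puts day 0 in the comparator.

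A reader might infer that the day of every dose is defined as control time. The documents do not support that. At 21 or 28 days the dose-2 day lies inside the dose-1 window of Table 3, and section 5.7.2.1 lets the windows overlap. Section 5.4.1 also treats control time between doses as unusual, whereas under this inference nearly every on-schedule recipient would have some. Nor does Table 6 help: taking the Moderna dose-2 day as control leaves 55 risk days, and 55/91 gives 282, 189, 88 and 261, not the tabulated 286, 191, 89 and 265. The dose-2 day is unassigned, no more.

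A reader might also infer a bias of 5-10%. The 4.9-10% range for the two-dose vaccines needs the dose-2 day to be control as well and no events on either day. It never applies to Janssen, and with dose-1 day 0 alone only the Moderna ITP worst case reaches 5%.

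Finally, the daily plot and the planned variation of control-interval lengths offer some protection. They may reveal a day-0 anomaly, but they leave the primary estimate as it is.

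**Conclusion.** The point holds for dose 1: sections 5.4.1 and 5.4.2 with Table 3 place day 0 in control time, in conflict with section 2.1 and with the purpose of exclusion (ii). For dose 2 the finding is only that the day has no stated status.

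The effect is small to moderate. With no events on dose-1 day 0, which is the extreme of depletion, the primary RR is inflated by 1.6% (Janssen, 28 days) to 5.0% (Moderna, 42 days). At an assumed threefold rate it is multiplied by 0.91-0.97, and a higher day-0 rate would lower it further, so the depletion bound does not cap that direction. The net sign cannot be known from the documents. The figures assume on-schedule doses, complete follow-up to day 90 counted from dose 1, and a constant baseline. If day 90 were counted from dose 2, the zero-event shift for the two-dose vaccines with one day 0 would be 63/62 to 49/48, or 1.6-2.1%.

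For scale, section 5.3 considers a possible 11% bias from claims delay worth quantifying. This one is smaller in the depletion direction under dose 1 alone, but it sits in the primary comparator and is cheap to remove.

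**What to change.** Reconcile sections 2.1, 5.4 and 5.4.1 so that they give one definition of control time and state the status of the dose-2 day.

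In sections 5.4.1 and 5.4.2, make day 0 of each dose an interval of its own, outside both risk and control time. Exclusion (ii) then works as intended, and the comparator treats day 0 in line with the plan's own 14-day pre-exposure exclusion. Report the day-0 event counts by AESI, brand and dose, and add one sensitivity analysis with day 0 counted as risk time.

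The cost is a sentence in each section, one more interval code, and the loss of 1-2 person-days per case with any events on them. The effect on Table 6 is negligible: on 90 observation days the required numbers are AMI 279/288, PE 182/193, DIC 79/90 and ITP 258/267, all within 2 cases of those stated.

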5.5.1 Primary Analysis: SCCS with Post-vaccination Control Intervals

Eligible vaccinees should meet the following inclusion/exclusion criteria.

Inclusion criteria:

- (i) Medicare beneficiaries enrolled in Part A (hospital insurance) and Part B (medical insurance) during the study observation period, as well as during the clean window prior to the occurrence of the AESI.
 - Continuous enrollment will be required from the start of an AESI's clean window relative to the occurrence of the AESI through day 90 post-vaccination, the end of the study period, disenrollment, or death, whichever comes first.
- (ii) Received at least one dose of a COVID-19 vaccine during the vaccination period of interest. The end of the vaccination period is defined as the vaccination cut-off date.
 - The vaccination cut-off date will be selected for each outcome to reduce the possibility of bias due to incomplete capture of events.
- (iii) For case population only, had a record of the AESI diagnosis during the study observation period.

Exclusion criteria:

- (i) Less than 65 years of age at the start of observation period.
- (ii) Does not contribute follow-up time to both risk and control intervals. If individuals disenroll, or reach the end of the study period during the risk window prior to accumulating any time for post-vaccination control intervals, they will be excluded.
- (iii) Had COVID-19 vaccination patterns that do not conform to expectations for the analysis of interest, e.g., doses that occur within a short time period following another dose or have a higher than expected dose number; more specific rules will be determined once more data on vaccination patterns are available.
- (iv) Had a diagnosis of the AESI during the AESI-specific clean window (Table 3) or during alternate clean windows assessed in sensitivity analyses.
- (v) Received different COVID-19 vaccines for the first and second dose. Based on the preliminary assessment, such a scenario only occurred in approximately 0.12% of cases with an AESI.

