Pulmonary Embolism (PE)	IP, primary diagnosis position
Disseminated Intravascular Coagulation (DIC)	IP
Disseminated Intravascular Coagulation (DIC)	IP, primary diagnosis position
Immune Thrombocytopenia (ITP)	IP
Immune Thrombocytopenia (ITP)	IP, primary diagnosis position

To assess the robustness of risk and control intervals, different lengths of the risk interval and the control interval will be explored with clinical input and consideration of empirical data from temporal clustering by plotting the distribution of incident AESI since vaccination and temporal scans to detect statistical clustering of events post vaccination. Given the potential carry-over effect, we will exclude a range of periods (e.g., 7, 14, and 21 days) after the end of the risk interval from contributing to the control intervals.

To assess the robustness of the analysis to potential violation of the assumption that exposures are independent of outcomes (e.g. AESI post first-dose may delay or preclude administration of the second-dose), a modified SCCS analysis will be conducted which adjusts for censored, perturbed or curtailed post-event exposures.²²

To assess the robustness of the analysis to the potential violation of the assumption that observation time is independent of outcomes (e.g. death post-AESI censors follow up time), a modified SCCS analysis will be conducted which removes the independence assumption.²³

To assess the robustness of the analysis to the potential under-capture of second doses administered by providers who do not submit insurance claims, a sensitivity analysis will be conducted removing projected second-dose exposed time potentially misclassified as control time among patients with only one observed dose. The empirical distribution of exposed time post-second dose will be assessed among patients with two doses, and the corresponding time will be excluded from the control time of patients with only one observed dose.

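### The primary SCCS cuts follow-up at death and leaves event-dependent second doses uncorrected; the one-dose RR is biased downward and the two-dose RR can err in either direction

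*Protocol*

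**What the plan says.** Section 5.4.1 starts observation at the first dose and counts post-vaccination time outside the risk windows as control time "until day 90 post-vaccination, end of study period, disenrollment, or death, whichever occurs first". It adds: "Individuals who only accrued data during the risk intervals will be ineligible to be included in the analysis". Exclusion (ii) in section 5.5.1 removes anyone who "Does not contribute follow-up time to both risk and control intervals". Its explanatory sentence names disenrollment and study end ("If individuals disenroll, or reach the end of the study period during the risk window prior to accumulating any time for post-vaccination control intervals") but not death.

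Section 5.7.2 fits a conditional Poisson model stratified by patient with log time as offset. The 95% confidence interval, the p-value and the attributable risk (AR) all come from that model.

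Section 5.7.2.1 recognises both weak points. For death after the event, "a modified SCCS analysis will be conducted which removes the independence assumption". For dose 2, it notes that an "AESI post first-dose may delay or preclude administration of the second-dose" and plans a second modified SCCS. Both are sensitivity analyses. Section 5.7.1 plans to count cases that died, but the protocol gives no case fatality or time to death.

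**The concern.** After a single dose, all control time comes after the risk window. A case that dies inside the risk window loses all its control time. A case that dies in the control window keeps its event and loses only the control time after death. Both effects lower the estimated RR, which in a safety study is the direction that hides harm.

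For two-dose vaccines there is an opposing error. A case whose event prevents dose 2 has less risk time and more control time than it would otherwise have had, which raises the RR.

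The conclusions and the AR rest on the uncorrected model, and no rule says which result prevails if the corrected analysis disagrees. Section 5.3, by contrast, quantifies a worst-case claims-delay bias of 11% and sets the data cut-off to limit it. Nothing comparable is done for death in AMI, PE and DIC at age 65 and over.

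**Working it through.** **1. The plan's own figure.** Table 6 gives 281 (28 risk days) and 286 (56 risk days) AMI cases for RR 1.42, 80% power, two-sided alpha 0.05. With r = risk days / observed days:

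- p = RR·r/(RR·r + 1 − r)
- A = 2[p·ln RR − ln(RR·r + 1 − r)]
- B = (ln RR)²·p(1 − p)/A
- n = (1.96 + 0.84·√B)²/A

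This gives 279 and 288 with 90 days, and exactly 281 and 286 with 91 days (days 0 to 90). Table 6 is therefore reproduced. It contains no allowance for death.

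**2. Inputs for the bias.** From the protocol: 28-day risk window (Table 3), 90-day observation (5.4.1), RR 1.42 (Table 6; section 5.8 assumes similar RRs for Moderna and Janssen), dose gaps of 21 and 28 days (Table 2). Assumed: case fatality, exponential time to death (mean 7 days unless stated), equal fatality in both windows, constant RR, day 0 not control time (section 2.1 places control time after the risk window).

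The estimate solves Σ[y − RR·t_r/(RR·t_r + t_c)] = 0, where y = 1 for an event in risk time and t_r, t_c are a case's risk and control days.

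**3. Hand check, one dose, true RR 1, 20% dying on the event day.**

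- Observed informative risk events: 0.8 × 28/90 = 0.249 of all cases.
- Expected at RR 1: 0.249 from survivors, plus fatal control-window cases, 0.2 × 62/90 × (28/62)·ln(90/28) = 0.138 × 0.527 = 0.073. Total 0.322.
- The equation balances at RR ≈ 0.68.

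**4. One dose, 28/90 days, mean 7 days to death.**

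| Assumed fatality | Estimate, true RR 1.00 | Estimate, true RR 1.42 | Power with 281 cases at the RR 1.42 estimate |
|---|---|---|---|
| 0% | 1.00 | 1.42 | 80% |
| 2% | 0.97 | 1.38 | – |
| 5% | 0.93 | 1.32 | 60% |
| 10% | 0.86 | 1.23 | 38% |
| 20% | 0.72–0.73 | 1.05 | 6% |

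Power is Φ[(√(nA) − 1.96)/√B] with r = 28/90. The delay to death matters: a true 1.42 falls to 1.05 at a fatality of 17.6% (death on the event day), 19.1% (mean 5 days), 21.4% (10 days) or 32.4% (30 days).

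**5. Which rule causes it.** A case with t_c = 0 contributes 1 − RR·t_r/(RR·t_r) = 0. Keeping or dropping risk-only cases therefore leaves the RR unchanged (1.034 both ways at 20% fatality and mean 5 days). The cause is censoring at death. The exclusion does remove fatal cases from the AR: about 15% of risk-window cases at 20% fatality and mean 7 days. With observation kept to its planned end and no one dropped, the one-dose model returns 1.42 at every fatality tested.

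**6. Two doses, no deaths, true RR 1.** Cases whose dose 2 is stopped have t_r = 28 instead of 49 (21-day gap) or 56 (28-day gap). If dose 2 is stopped in 25, 50 or 100% of cases with an event before it, the estimate is about 1.06, 1.12 or 1.26 (21 days) and 1.11, 1.24 or 1.54 (28 days).

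**7. Both errors together, true RR 1.42, 10% fatality, mean 7 days.**

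| Dose 2 stopped | 21-day gap | 28-day gap |
|---|---|---|
| 0% | 1.26 | 1.27 |
| 25% | 1.34 | 1.43 |
| 50% | 1.43 | 1.62 |
| 100% | 1.64 | 2.08 |

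**8. Ignoring death in the standard two-dose model.** If follow-up simply runs to day 90, a death before dose 2 still removes dose 2. At 20% fatality the estimate is about 1.47 to 1.48 (21 days) and 1.54 to 1.55 (28 days), so this shortcut overcorrects.

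**The case against.** The strongest reply is that the protocol already commits to both corrections in 5.7.2.1, so only the choice of primary analysis is in dispute. The exploratory SCRI also waives exclusion (ii) and uses pre-vaccination control time, to which fatal risk-window cases can contribute. That is true, and the protocol does not overlook the problem. It still leaves the primary test and AR on the model whose assumptions it doubts, with no rule for disagreement.

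Four stronger readings are tempting, and the documents do not support them:

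- **A true 1.42 will be reported as 1.05.** This needs roughly 20% fatality in the one-dose layout. The protocol gives no fatality; at 5% the estimate is about 1.32.
- **The Pfizer-BioNTech signal will be hidden.** The 1.42 was observed for that two-dose vaccine, and section 1 reports no signal for Janssen. In the two-dose layout the errors oppose each other, so the net direction is unknown.
- **Excluding risk-only cases causes the RR bias.** It does not change the RR. Nor do all fatal risk-window cases disappear: only those who die before any control time accrues.
- **Section 5.1 is wrong to say "Post-vaccination control intervals will avoid such a bias of reverse causation".** In context this refers to events before vaccination. The sentence is at most incomplete for the time between doses.

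**Conclusion.** The concern holds in conditional form. For a one-dose vaccine, censoring at death biases the primary RR downward. At an assumed 10% fatality and mean 7 days to death the shortfall is about 14% (0.86 for a true 1.00; 1.23 for 1.42), more than the 11% claims-delay bias that section 5.3 takes care to limit. At 2% fatality it is small (1.38 for 1.42).

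For two-dose vaccines the primary RR can be too low, about right or too high, depending on fatality, how often dose 2 is stopped, and the dose gap. The mechanism and the one-dose direction follow from the design; every magnitude rests on the assumptions in the working. The AR additionally loses fatal cases that never reach control time.

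**What to change.** For AMI, PE and DIC, make the corrected analyses primary, or co-primary with a stated rule on which result prevails, and report the standard model as the sensitivity analysis. Split by brand:

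- **Janssen:** the windows are fixed by the vaccination date, so end observation at the planned day 90 or study end regardless of death, and keep fatal risk-window cases in the RR and AR.
- **Pfizer-BioNTech and Moderna:** use the event-dependent-exposure SCCS already planned in 5.7.2.1, with planned end of observation. Do not simply ignore death in the standard model.

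Also state how exclusion (ii) treats death, report fatal cases excluded by interval, and qualify the 5.1 sentence for the time between doses.

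No new data are needed, and the change builds largely on methods the protocol already commits to. It is more than relabelling: the planned-end rule must be written into 5.4.1 and 5.5.1, and the two-dose analysis must be specified as one primary estimator. The price is wider intervals and somewhat more modelling.
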